Models of Care in the Transition from the Secondary to the Primary Sector among the Frailest Elderly +75; a Randomized Controlled Trial

[name]

Aarhus University Hospital

Randers Regional Hospital

Aarhus University

February 8th, 2019

Models of Care in the Transition from the Secondary to the Primary Sector among the Frailest Elderly +75; a Randomized Controlled Trial

In most Western countries the elderly population increases rapidly. In Denmark, the population of elderly aged 75 years or older may amount to nearly 15 % of the entire population in 2050 compared to 9 % today (2017) (1). A large part of the elderly population is at high risk of hospitalization including more admissions and increased morbidity and mortality (2,3). The number of hospital beds is declining persistently (4), calling for shorter lengths of stay (LOS) (5,6).

Increasingly complex treatments now take place outside hospital. Presently, many Danish regional hospitals establish geriatric wards and other geriatric in-hospital and outpatient services to overcome these challenges. The aim of the present PhD-study is to investigate the effects of different models of transitional care among the frailest elderly patients.

Readmission

Readmitted patients occupy many beds and other hospital resources. Patients are at a risk of high mortality (7) and decline of functional ability (8,9). More than 20 % of Danish medical patients aged 65 years or older become readmitted within 30 days after discharge (10), more frequently in the frail elderly (11). The risk of readmission is particularly high within the first week after discharge, where more than 40% of readmissions happen (12,13). Many reasons and factors for readmissions have been mentioned (11,14-16) such as: former or recent admission, duration of the index hospitalization, degree of comorbidity and low functional ability (11,15). To prevent readmissions it is important to identify the reason for admission and remove it, to ensure that the correct medication is implemented and make sure that adequate social service is provided, to convey unsolved problems to the primary care, ensure continuity during transfer and finally establish sufficient and timely follow-up after discharge (11,14-17).

Identification of patients at risk

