All frail patients admitted to the ED and the Department of Geriatrics are randomized 1:1 to one of two different follow-up efforts prior to CGA performed during hospitalization. Thereby the intervention is randomly split into two groups:

- An intervention (I) consisting of CGA during hospitalization and early post-discharge follow-up care by a community nurse and a GP
- An intervention (II) consisting of CGA during hospitalization and early post-discharge follow-up care, including continued CGA and tailored follow-up care, by a geriatric team

The intervention cohort will be compared to a control cohort consisting of similar frail elderly who receive usual care without involvement of geriatric care during hospitalization and after discharge.

Hypotheses

- The geriatric team follow-up is as effective as a community nurse and GP follow-up measured by readmission, mortality, LOS, direct discharge from ED and physical functional recovery
- The effects of three transitional follow-up approaches (community nurse and GP; multidisciplinary geriatric team; usual care) are similar measured in terms of readmission, time at home, duration of readmission, LOS, direct discharge from ED, mortality and PROMs
- When stratified into subgroups with regards to level of frailty (moderate and severe) and type of dwelling, the geriatric team follow up is as good as community nurse and GP follow-up measured by readmission, mortality, LOS, direct discharge from ED and physical functional recovery

Methods

Design

The first study is conducted as a randomized controlled trial (RCT) using two different degrees of intervention. The second study is a cohort study where the two groups in the RCT are compared to an unexposed control group. The third study is sub-group analyses of the RCT data according to frailty status and type of dwelling.

Study population

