The population allocated to intervention comprises geriatric patients acutely admitted to the ED, Aarhus University Hospital (AUH) or transferred to one of the two geriatric wards at AUH. Subjects are included immediately on the day of admission at the ED, AUH and the Department of Geriatrics (wards 1 and 2), AUH, as shown in Fig. 1. Patients admitted to the ED at night and promptly discharged before enrollment to the intervention cohort can be performed the following day are not included. Likewise, patients to the control group are included immediately on the day of admission at the ED, Randers Regional Hospital (RRH), and at the medical wards 1, 2, 3 and 4, RRH. Patients transferred to other departments are excluded. Patients can only be included once. Enrollment and randomization to the intervention group are performed by therapists working in the ED or the geriatric wards. Enrollment to the control group is done by a Research Assistant. In the control group frailty screening is done by the PhD-student using a frailty screening tool based exclusively on data collected through medical records. The frailty screening tool will be validated by crosschecks performed by a blinded project Research Assistant. The results of the validation study will be analyzed and published during 2019.

Inclusion criteria:

- Aged 75 years or older
- Living within the municipality of Aarhus (except for the control group, see below)
- MPI-score = 2 (moderate frailty) or MPI score = 3 (severe frailty)

Exclusion criteria:

- Included in any other kind of follow-up schemes
- Declared terminally ill or undergoing palliative care at admission
- Admitted from one specific temporary nursing home with geriatric medical assistance (Vikærgården)
- Discharge or transfer to another department, including hospice
- MPI-score = 1 (low frailty)
- Discharged to one specific temporary nursing home with geriatric medical assistance (Vikærgården)
- The patient does not want a visit after discharge

Inclusion- and exclusion criteria to the control group are the same as for the two intervention groups, except that subjects eligible for the control group are living within the four municipalities of RRH: Randers, Favrskov, Norddjurs and Syddjurs.

Randomization

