The patients in the control group are discharged to usual care and do not receive early follow-up visits. Usual care features municipality services and optionally a GP home visit (see Appendix 2). Eligible control patients are consecutively included by a Research Assistant. The estimated level of frailty will be assessed by the PhD-student based on a MPI-screening tool fitted to be performed using only medical record data. This fitted tool will be tested and validated prior to the inclusion of the control group. Clinicians will be blinded to the result of the MPI-screening of the control subjects to ensure that discharge is performed in accordance with usual care.

Outcomes

The primary outcome is readmission within 30 days after discharge. Secondary outcomes are:

- Mortality 30 days after discharge and 90 days after admission
- Length of stay during primary admission and total length of stay including following readmissions
- Direct discharge from the Emergency Department
- Time at home before readmission
- Duration of readmission
- Physical functional status 30 days after discharge (Functional Recovery Score)
- Patient Related Outcome Measures as defined by a focus group of included patients and/or their relatives

Statistical analyses

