Data are registered in REDCap and exported to STATA version 15 for the statistical analyses. Statistical significant results are defined as a p-value of 5% or less. The two intervention groups and the control group will be compared with regard to baseline measures. If needed, statistical corrections for demographical differences and level of frailty will be made. The use of services and other contents of follow-up will be assessed and compared if possible. Baseline data collected for the entire study population before discharge are: age, gender, date of admission, co-habitation status, number of drugs, and level of frailty measured by MPI including functional status by means of Functional Recovery Score (FRS) at discharge. Follow-up data for the control group will be collected on type of planned care after discharge. Follow-up data for the entire study population will be collected on: department of discharge, date of discharge, primary diagnosis at discharge, dwelling after discharge, readmission date, and death date. For the intervention cohort additional data are collected: date of follow-up, provided services after discharge, number and date of visits (team, GP, nurse) after discharge, phone-calls to the geriatric team or GP, nutritionist consultations, FRS after 30 days, date of dispatch of discharge summary. Additional data will be collected by review of the electronic patient records.

Outcomes

A hazard ratio (HR) for readmissions will be calculated using a Cox regression model with death as a 'competing risk' factor. The HRs of readmission with 95% confidence intervals (95% CI) for interventions I and II will be compared individually and to the control group. The interventions will be tested in subgroup analyzes based on: patients discharged directly from the ED, type of dwelling and level of frailty. Median LOS, time at home before readmission and duration of readmission will be calculated and compared using the Wilcoxon rank-sum test. The mortality hazard ratio will be calculated also using the Cox regression model. The change in functional status at discharge and 30 days after discharge will be compared in a linear regression model. Data will be analyzed in accordance with intention-to-treat and per-protocol analysis.

Sample size

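### The usual-care comparison (Study 2) neither lists nor adjusts for prior admission, a readmission factor the protocol itself names, so it is open to residual confounding of unknown size and direction

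*Protocol*

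**What the plan says.** The Design section of the Protocol describes Study 2 in these words: "The second study is a cohort study where the two groups in the RCT are compared to an unexposed control group". The controls come from a different catchment. The Study population section states that "subjects eligible for the control group are living within the four municipalities of RRH: Randers, Favrskov, Norddjurs and Syddjurs", while the randomised patients live in Aarhus municipality. The wards differ too: the emergency department and four medical wards in Randers, against the emergency department and two geriatric wards in Aarhus.

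The primary outcome is readmission within 30 days of discharge. Among factors that have been linked to readmission, the Readmission section gives as examples "former or recent admission, duration of the index hospitalization, degree of comorbidity and low functional ability".

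Statistical analyses itemises the baseline data for all patients as "age, gender, date of admission, co-habitation status, number of drugs, and level of frailty measured by MPI", the last including the Functional Recovery Score (FRS) at discharge. Follow-up data for all patients are "department of discharge, date of discharge, primary diagnosis at discharge, dwelling after discharge, readmission date, and death date". The section adds that further data will come from the electronic patient records, without naming any item. On adjustment it says only: "If needed, statistical corrections for demographical differences and level of frailty will be made". The Cox model for readmission names no covariates.

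On timing, the Control group section says of the records-only frailty tool: "This fitted tool will be tested and validated prior to the inclusion of the control group". No matching wait is stated for the randomised arms, and enrolment dates are given for neither cohort.

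The combined protocol and SAP carries the same adjustment sentence, data lists and validation sentence.

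**The concern.** Randomisation does not protect the comparison with usual care, so its credibility rests on the adjustment set. The plan names a prognostic factor for its own primary outcome and then provides no variable for it. If patients in Aarhus and Randers differ in recent admissions beyond what demographics and frailty explain, that difference passes into both hazard ratios against usual care and could be read as an effect of the intervention, or could hide one.

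Two features add to this. Adjustment is conditional, with no rule for when it is needed or which terms then enter, so the adjustment set can be chosen after the data are seen. Calendar time is also absent from the correction, although date of admission is collected and the controls alone must wait for the tool to be validated.

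**Working it through.** **1. Are the named factors covered?** Setting the Readmission section against Statistical analyses and Appendix 1A:

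| Factor named in the Protocol | Variable available from the listed data |
|---|---|
| Former or recent admission | None |
| Duration of index stay | Derivable from admission and discharge dates |
| Comorbidity | Cumulative Illness Rating Scale domain of MPI |
| Low functional ability | ADL and IADL domains of MPI; FRS |

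The eight MPI domains are cognition, pressure-sore risk, ADL, IADL, comorbidity, nutrition, number of drugs and social status. None counts admissions. The nearest item is one nutritional-assessment question on psychological stress or acute disease in the past three months.

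**2. The plan's own figure.** No sample size is given for Study 2. The 758 per arm concerns I against II. With 13.7% v 8%, two-sided 5%, 90% power and a continuity correction, n = 659 per arm, and 659 × 1.15 = 757.85, i.e. 758. The figure reproduces and is not disputed. It is used below only as an assumed group size.

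**3. Crude bias from one unmeasured binary factor.** With prevalence p1 in the intervention group, p0 in controls, and risk ratio RR for readmission,

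B = (1 + p1(RR − 1)) / (1 + p0(RR − 1)).

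The documents give none of these inputs. Assumed: RR 1.5, 2 or 2.5; prevalence equal, or differing by 10 points (35% and 45%) or 20 points (30% and 50%), in either direction.

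| RR | Equal | 35% v 45% | 30% v 50% | 45% v 35% | 50% v 30% |
|---|---|---|---|---|---|
| 1.5 | 1.00 | 0.96 | 0.92 | 1.04 | 1.09 |
| 2.0 | 1.00 | 0.93 | 0.87 | 1.07 | 1.15 |
| 2.5 | 1.00 | 0.91 | 0.83 | 1.10 | 1.21 |

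For example, at RR 2.5 and 30% v 50%: (1 + 0.30 × 1.5) / (1 + 0.50 × 1.5) = 1.45 / 1.75 = 0.83. A factor below 1 flatters the intervention; above 1 it penalises it.

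**4. What that does to the test.** Assume 758 per group (controls included), no true effect, and a normal-approximation test of two proportions at two-sided 5%. Control risk is taken as 13.7% (pilot, intervention I) or 20% (the Readmission section gives more than 20% for Danish medical patients aged 65 or older).

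| B | Chance of p < 0.05, control risk 13.7% | Control risk 20% |
|---|---|---|
| 0.93 | 8% | 10% |
| 0.87 | 19% | 26% |

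The nominal rate is 5%.

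**5. Limits.** These are crude factors. They treat prior admission as unrelated to anything already adjusted for, so the residual bias is nearer 1 to the extent that frailty and drug count carry the same information. No figure is offered for calendar time, because the documents give no enrolment dates to base one on.

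**The case against.** A reader might infer that the usual-care contrasts must remain confounded whatever model is fitted. The documents do not support that, for four reasons.

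- The Protocol provides for further data from electronic records, so the itemised lists are not shown to be exhaustive and prior admissions could still be collected. Date of admission is already listed for everyone, so calendar time can be modelled with no new data.
- Confounding needs a difference between the cohorts beyond what the adjusted variables explain. No prevalence is reported for either hospital, and balance is possible.
- MPI includes comorbidity, function, nutrition and drug count, and the Protocol's Conclusion section says MPI has predicted readmission. Correcting for frailty may remove part of any bias.
- The validation sentence does not show that enrolment periods differ, only that they may.

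The Readmission list is also illustrative and does not rank its factors.

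All of this stands, and it limits the point to pre-specification and a risk of residual confounding. It does not remove the point. The record-review sentence names neither an item nor a covariate, and the correction sentence leaves prior admission out even if the item is collected. Frailty is an imperfect proxy, more so because controls are graded from records alone while the randomised patients are not.

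**Conclusion.** The concern holds as a gap in the Study 2 adjustment plan. Prior admission is named as relevant to the primary outcome but is neither listed as data nor specified as a covariate, and the adjustment that is specified is conditional. The two contrasts with usual care on 30-day readmission are therefore open to residual confounding of unknown size and direction.

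On the assumed inputs the crude bias factor lies between 0.83 and 1.21, is 1.00 if the cohorts are balanced, and shrinks towards 1 as far as frailty and drug count act as proxies. These figures illustrate what is possible and do not estimate what will occur. Randomisation protects I against II, and the 758 per arm is not in question.

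**What to change.** 1. Name the number of acute admissions in the 12 months before the index admission as an item in the planned record review, for all patients at both hospitals. Take it from admission records. The usual-care screening described in Appendix 2 uses former admissions in the past year, but the same appendix says screening is sometimes given low priority, so the screening form is not a reliable source.
2. Replace the conditional correction sentence with a fixed set: every Study 2 readmission model includes prior admissions, age, gender, frailty level and calendar month or season of admission, whatever the baseline comparisons show.
3. If enrolment periods turn out to differ, report a sensitivity analysis restricted to the months in which both cohorts enrolled, as far as numbers allow.

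The cost is one extra field from records already due for review and a few model terms, with no patient contact. The event count should bear this: on the plan's own rates, the randomised arms alone would yield about 659 × 0.137 + 659 × 0.08 = 90 + 53 = 143 readmissions before any controls are counted. Adjustment will not remove differences in unmeasured factors, so Study 2 should still be reported as an observational comparison.

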As shown in Fig. 2, all intervention group patients are allocated at the time of randomization on the day of admission to receive either early visit from the community nurse (I) or the multidisciplinary geriatric team (II). The randomization is stratified with regard to dwelling (living alone; cohabiting; nursing home) and number of drugs prescribed prior to

admission (0-3, 4-7, 8 or more drugs), and conducted using the randomization function in REDCap (49). Randomization is open throughout the whole admission with the purpose to enable early discharge planning.

Intervention I and II

Both intervention groups are assessed according to CGA, either by the geriatrician and the physiotherapist/geriatric nurse in the ED, or by a multidisciplinary team comprised of geriatricians, specialized nurses, physiotherapists and occupational therapists during hospitalization in the geriatric wards.

- Intervention (I): comprises early follow-up visit from the community nurse within 24 hours after discharge, and the possibility of consulting a nutritionist, thus supplementing usual care services including the possibility of consulting the patients' GP. Responsibility of treatment including implementation of suggested initiatives and any further assessment is handed over to the GP at discharge.
- Intervention (II): CGA is continued during early follow-up by the geriatric team. On weekdays visits are scheduled within 24 hours after discharge. For patients discharged during weekends or holidays, supporting telephone calls are provided by the geriatric team. If needed, the geriatric team nurse visits the patient. The concept of CGA in this stage does not differ from the above-mentioned. There are no standardized demands, but a part of the intervention can be to perform hospital services at home and continued treatment and diagnostics after discharge. The possible services provided by the geriatric team are further described in the geriatric team course description. The responsibility of treatment rests with the geriatric team until dispatch of the discharge summary. Patients then return to usual care. The geriatric team follow-up is planned to last a maximum of 7 days, yet allowing extension for as long as there is a need for services performed exclusively by the geriatric team as described in the geriatric team course description.

Control group

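### The subgroup discharged directly from the ED is formed after open randomisation and is itself an outcome, so its I-versus-II readmission hazard ratio is not protected by randomisation

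*Protocol*

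**What the plan says.** The relevant text is nearly identical in the Protocol and in the Combined protocol and SAP.

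- **Subgroups** (Statistical analyses, Outcomes): "The interventions will be tested in subgroup analyzes based on: patients discharged directly from the ED, type of dwelling and level of frailty".
- **The same variable as an outcome** (Outcomes, secondary list): "Direct discharge from the Emergency Department". The first hypothesis also compares the arms on it: "The geriatric team follow-up is as effective as a community nurse and GP follow-up measured by readmission, mortality, LOS, direct discharge from ED".
- **Where patients are enrolled** (Study population): "Subjects are included immediately on the day of admission at the ED, AUH and the Department of Geriatrics (wards 1 and 2), AUH".
- **When they are randomised** (Objectives): patients are "randomized 1:1 to one of two different follow-up efforts prior to CGA performed during hospitalization".
- **Allocation is known** (Randomization): "Randomization is open throughout the whole admission with the purpose to enable early discharge planning".
- **What each arm offers after discharge** (Intervention I and II): in arm II, "a part of the intervention can be to perform hospital services at home and continued treatment and diagnostics after discharge"; in arm I, "Responsibility of treatment including implementation of suggested initiatives and any further assessment is handed over to the GP at discharge".

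The Design section and the third hypothesis name only frailty and dwelling as subgroups. Statistical analyses lists the department of discharge among the follow-up data, not the baseline data.

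**The concern.** A subgroup keeps the protection of randomisation only if membership is fixed before, or cannot be influenced by, the allocation. Dwelling and MPI level, taken at enrolment, meet that condition. Direct discharge from the ED does not. A patient enrolled in the ED is randomised first. Staff who know the arm then decide whether the patient goes home or moves to a ward. A patient enrolled on a geriatric ward has already left the ED, so this subgroup contains only patients for whom the decision came after allocation.

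The plan itself gives a plausible reason why selection might differ: one arm can bring hospital-type services into the home, while the other passes responsibility to the GP. If staff send home a different mix of patients in each arm, and that mix differs in prognosis, the two sides of the subgroup are no longer comparable.

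At stake is the reading of one hazard ratio. Statistical analyses sets a 5% significance threshold and does not mark any subgroup as exploratory. The Objectives include finding out who benefits most from each approach. A significant result here could be read as showing which follow-up model suits patients sent straight home, when it may partly show who was sent home.

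**Working it through.** **The plan's own figure.** The documents give no number for this subgroup. The whole-trial size reproduces from the pilot readmission rates of 13.7% and 8%, power 90%, 5% two-sided (sidedness assumed):

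n = [1.960 √(2 × 0.1085 × 0.8915) + 1.282 √(0.137 × 0.863 + 0.08 × 0.92)]² / 0.057² = 623.6, rounded up to 624.

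With continuity correction: (623.6/4) × [1 + √(1 + 4/(623.6 × 0.057))]² = 658.2, rounded up to 659. Then 659 × 1.15 = 758, as stated. So 758 already contains the allowance for drop-out and mortality.

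**Illustration of the mechanism.** Every input below is an assumption.

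- No true effect of arm II versus arm I.
- Mean 30-day readmission risk 13.7%; risk normal on the logit scale with SD 1.0.
- 49% sent home directly in arm I, and 49% or 56% in arm II. These percentages are borrowed from an earlier study cited under Outcome measures; its contrast was geriatric follow-up against usual care.
- Discharge score = c·z + √(1 − c²)·e, where z is the standardised logit risk and e is independent noise. Each arm sends home its lowest-scoring share, so c measures how strongly discharge route follows risk.
- Test: z-test of the log risk ratio at two-sided 5%, with SE = √[(1 − p₁)/(n₁p₁) + (1 − p₂)/(n₂p₂)].
- Patients per arm to whom the discharge shares apply: 758, 659, or about 330 (half of 659 enrolled in the ED, since the ED share is not given).

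| c, arm I / II | Sent home, I / II | Readmission risk, I / II | False ratio II/I | Type I error at 758 / 659 / 330 |
|---|---|---|---|---|
| same c | 49% / 49% | equal | 1.00 | 5.0% at each |
| 0.3 / 0.3 | 49% / 56% | 11.14% / 11.45% | 1.03 | 5.2 / 5.2 / 5.1% |
| 0.5 / 0.5 | 49% / 56% | 9.46% / 9.93% | 1.05 | 5.6 / 5.5 / 5.2% |
| 0.7 / 0.7 | 49% / 56% | 7.82% / 8.41% | 1.08 | 6.1 / 5.9 / 5.5% |
| 0.6 / 0.5 | 49% / 49% | 8.64% / 9.46% | 1.10 | 6.8 / 6.6 / 5.8% |
| 0.7 / 0.5 | 49% / 49% | 7.82% / 9.46% | 1.21 | 12.5 / 11.5 / 8.2% |
| 0.5 / 0.7 | 49% / 49% | 9.46% / 7.82% | 0.83 | 12.5 / 11.5 / 8.2% |
| 0.7 / 0.5 | 49% / 56% | 7.82% / 9.93% | 1.27 | 18.0 / 16.2 / 10.5% |
| 0.5 / 0.7 | 49% / 56% | 9.46% / 8.41% | 0.89 | 8.2 / 7.7 / 6.4% |
| 0.50 / 0.562 | 49% / 56% | 9.46% / 9.46% | 1.00 | 5.0% at each |

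Worked example, sixth row at 758: n = 0.49 × 758 = 371 per arm. SE = √[0.9218/(371.4 × 0.0782) + 0.9054/(371.4 × 0.0946)] = 0.240. The log ratio is ln 1.21 = 0.190, or 0.79 SE. The rejection probability is Φ(−1.96 + 0.79) + Φ(−1.96 − 0.79) = 12.5%. On the hazard scale the same risks give ln(1 − 0.0946)/ln(1 − 0.0782) = 1.22, so the risk ratio is a fair stand-in for the planned hazard ratio.

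For that row, changing one input at a time gives 1.13 at SD 0.7, 1.36 at SD 1.5, 1.38 at a 20% base and 1.17 at a 60% base.

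**What the table shows.** With the same ranking in both arms, the distortion is small. With equal rates but different rankings, it can be larger and go either way. In the last row the arms differ in both rate and ranking, yet the errors cancel.

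**The case against.** The strongest case against has four parts.

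- **Nothing shows that selection differs between I and II.** Both arms receive the same in-hospital CGA, the first hypothesis expects equality on direct discharge, and no I-versus-II figure is given. This stands as a limit on size. It does not restore the protection, because a hypothesis of equality is not evidence of it, and equal rates can hide a different mix.
- **The larger figures rest on an unsourced input.** The difference in c between arms appears nowhere in the documents. This stands, which is why the table is only an illustration.
- **The type I errors depend on a subgroup size that is not given.** Applying 49% to all 758 overstates it, because some patients are enrolled on the wards and 758 includes the allowance. This stands, so smaller sizes are shown. The false ratios do not depend on size.
- **Little hangs on it.** No stated hypothesis uses this subgroup. This stands and lowers the severity.

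The planned intention-to-treat analysis does not answer the point, because the selection occurs within the randomised arms. The adjustment for demographics and frailty, made only if needed, might reduce a bias but cannot be relied on to remove it.

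A reader might also infer from the cited rise from 49% to 56% that arm II will discharge more patients directly than arm I. The documents do not support that: the Sample size section describes the earlier studies as comparing early geriatric visits with usual care in patients selected by diagnosis.

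**Conclusion.** The point holds as a structural weakness of one planned subgroup test. The I-versus-II readmission hazard ratio among patients discharged directly from the ED lacks the protection of randomisation. It can be biased when the arms differ in whom they send home and those patients differ in prognosis.

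Two stronger readings are tempting and are not supported. The first is that this hazard ratio must be biased whenever selection differs; the cancelling case in the table shows otherwise. The second is that the trial's main result is compromised. The overall I-versus-II comparison and the subgroups by baseline dwelling and MPI do not condition on discharge route. The comparison with the control cohort is non-randomised in any case and is not part of this point.

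Size and direction cannot be determined from the documents. Under the assumed inputs, the false ratio is 1.00 to 1.08 with type I error of about 5% to 6% if both arms rank patients alike. With c of 0.7 against 0.5, it runs from 0.83 to 1.27, with type I error between 6.4% and 18% depending on direction, shift and subgroup size. Severity is minor to moderate.

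**What to change.** In the Outcomes paragraph of Statistical analyses, in both documents, do one of the following:

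1. Remove direct ED discharge from the subgroups tested between arms. This also brings the paragraph into line with the Design section and the third hypothesis.
2. Keep it, but label it descriptive and non-randomised, with no between-arm p-value.

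Either way, keep direct ED discharge as a secondary outcome.

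If a subgroup by setting is wanted, use place of enrolment at randomisation (ED or geriatric ward). The baseline data list does not name this variable, but it can be taken from the enrolment record or from the electronic patient records, which the plan already intends to review.

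The cost is one sentence per document and, at most, one data field. Recruitment, care and sample size do not change. The downside is that place of enrolment answers a slightly different question, since a patient enrolled in the ED may later move to a ward.
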